	
During Procedure (up to 2 ELS treatments):
 
Cystoscopy with local anaesthesia and light or moderate sedation or light general anaesthesia (investigator's discretion), placement of ureteral catheter, periodic fluoroscopic and/or diagnostic ultrasound imaging (at investigator's discretion), intraluminal ureteral placement of ELS Acoustic Enhancer material and administration of acoustic energy. Multiple repetitions of ELS Acoustic Enhancer placement-insonation cycle will be performed
 
Follow-up:
 
1, 2, 3, 7 days (telephone follow-up): Assess pain and pain medications, evaluate for AEs
 
14 (\pm 4) days (on site exam): KUB X-ray and ultrasound; physical exam; assess pain and pain medications; urine culture; evaluate for AEs; Assess for eligibility for 2nd ELS Treatment (i.e. treated stone/fragment is \geq 3 mm and subject remains eligible per I/E criteria)
 
30 (\pm 4) days after last ELS procedure: CT scan (non-contrast) to evaluate stone status; physical exam; assess pain and pain medications; evaluate for AEs; serum creatinine; Assess for eligibility for 2nd ELS Treatment
 
Treatment 2 (if necessary): Repeat ELS treatment if subject meets eligibility criteria (i.e. treated stone/fragment is \geq 3 mm and subject remains eligible per I/E criteria). If performed, repeat Day 1, 2, 3, 7, 14 & 30 Follow-Up visits
 
90 (\pm 21) days: physical exam; serum creatinine; evaluate for AEs and record medications; renal-bladder ultrasound for safety assessment

Primary Endpoint	Treatment success: Proportion of study participants who, after up to 2 ELS treatments, have a complete absence of stones or with any residual fragments measuring less than 3 mm in the largest dimension as assessed by follow-up imaging through 30 day follow-up after last ELS procedure
Secondary Endpoints	
 • Proportion of participants with Serious Device and/or Serious Procedure-Related AEs from initial ELS Treatment through 30 days following last ELS treatment • Proportion of participants with Serious Device and/or Serious Procedure-Related AEs from initial ELS Treatment through 90 days following last ELS treatment • All AEs & SAEs from initial ELS Treatment through 30 days following last ELS treatment • All AEs & SAEs from initial ELS Treatment through 90 days following last ELS treatment • Participant satisfaction at 30 day follow-up following last ELS treatment

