4.3 Eligibility Criteria

4.3.1 Inclusion Criteria

1. Participant is ≥ 18 years
2. Participants has voluntarily signed/dated the informed consent form.
3. Participant understands and accepts the study requirements.
4. Participant has one urinary stone eligible for treatment (minimum) that is:
 - a. apparent on a computed tomography (CT) scan within 14 days prior to study enrollment,
 - b. located within the renal pelvis or ureter, and,
 - c. is ≥ 3 mm in all dimensions
 - d. is ≤ 10 mm in maximum dimension and has area $<56 \text{ mm}^2$, as estimated by pre-procedure CT (area calculation: product of mathematical constant pi and the square of the radius for a stone appearing approximately circular on CT; product of long dimension and short dimension for a stone appearing oblong on CT)
5. Participants with additional stone(s) in one or both kidneys are admissible and must meet the following inclusion criteria:
 - a. Number of stones (≥ 3 mm) present on treated side is 2 or less
 - b. Untreated stones must not be anticipated to require treatment within 30 days of enrollment, as determined by the investigator

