5. STUDY ENDPOINTS

5.1 Primary Endpoint

Treatment success: Proportion of study participants who are successfully treated following up to 2 ELS treatments [defined as absence of stones or with remaining fragments of less than 3 mm on the largest dimension by follow-up imaging through 30 day visit after last ELS procedure].

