6.4 Non-ELS Treatment stone interventions

Participants may require intervention other than ELS Treatment to resolve their condition as it relates to their urinary stone(s) selected for ELS Treatment. This study requires one additional ELS Treatment to be performed if needed, as discussed in the section above. These additional stone interventions will be recorded on the appropriate eCRF. Adverse events will be assessed using the definitions in Section 8.1.

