11.3 Primary Endpoint

The study’s primary endpoint is treatment success, which is the proportion of study participants who are successfully treated following up to 2 ELS treatments. This is defined as absence of stones or with remaining fragments of less than 3 mm on the largest dimension by follow-up imaging through 30 day visit after last ELS procedure. If ELS Treatment was performed on two stones in one participant, both stones/fragments need to meet the endpoint to be counted as a success.

The study will test the statistical hypothesis that the treatment success rate is not inferior to the performance goal defined using published AUA treatment guidance (64%). Formally, the null and alternative hypotheses are as follows:

$$H_0: p < PG$$

$$H_A: p > PG$$

where p is the success rate observed in the prospective study outcomes and PG is the performance goal. The PG in turn is computed as:

$$PG = r - p - \Delta,$$

where r is the reference rate, p is a correction for differences in treatment success definitions and Δ is the statistical testing margin. These values are further defined as follows:

- $r = 64\% = 0.64$ is the reference rate derived from AUA guidance [13]
- $p = 4\% = 0.04$ is a correction factor for the difference between the definition of treatment success in the literature reference and the definition in the study protocol. Specifically, the reference rate is measured after any number of treatments, while the investigational protocol permits at most two treatments before treatment effectiveness is measured.
- $\Delta = 10\% = 0.10$ is the statistical testing margin for comparison.

Hence $PG = r - p - \Delta = 64\% - 4\% - 10\% = 50\% = 0.50$ in the primary endpoint hypothesis testing. The hypothesis test will be performed by comparing the observed success rate to the PG via exact binomial methods, where a lower two-sided 95% exact confidence bound exceeding the PG will constitute rejection of the null hypothesis.

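### The plan has no rule for scoring a participant whose ELS-treated stone is cleared by a non-ELS procedure before the endpoint imaging; read literally, the imaging definition would count a success

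*Combined protocol and SAP*

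**What the plan says.** The endpoint is stated three times, each time by what imaging shows after at most two ELS treatments. Section 5.1 defines success as "absence of stones or with remaining fragments of less than 3 mm on the largest dimension by follow-up imaging through 30 day visit" following the last ELS procedure. The synopsis has "complete absence of stones or with any residual fragments measuring less than 3 mm in the largest dimension as assessed by follow-up imaging", with the same window. Section 11.3 repeats the definition and adds one scoring rule, for participants with two treated stones: "both stones/fragments need to meet the endpoint to be counted as a success".

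Section 6.4 expects other procedures on the target stone: "Participants may require intervention other than ELS Treatment to resolve their condition as it relates to their urinary stone(s) selected for ELS Treatment". On handling, it says that "These additional stone interventions will be recorded on the appropriate eCRF" and that adverse events are assessed under the usual definitions. It gives no consequence for the endpoint.

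The remaining sections do not fill the gap:

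- Section 6.3.1 asks the investigator to document why an eligible participant did not have a second ELS treatment, but gives no outcome rule.
- Section 11.1 puts all enrolled participants and all available data in the ITT analysis. Its per-protocol set does not name non-ELS intervention as a reason for exclusion.
- Section 11.5 covers missing data, not outcomes observed after another procedure.
- Section 11.7 promises a separate SAP, which is not among the documents.

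**The concern.** The window is tied to the last ELS procedure, so an intervening ureteroscopy or SWL neither ends nor resets it. A participant in whom ELS failed and another procedure worked can reach the 30-day CT without stones. The imaging wording then fits, and no rule takes that participant out of the numerator.

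This matters because the trial has one arm and a fixed goal. No control group carries the same bias, so every rescued failure scored as a success moves the result towards a pass. It also undercuts the plan's own reasoning. Section 11.3 lowers the reference rate by 4 points because the literature allows any number of treatments and this protocol at most two. Crediting a further, non-ELS procedure gives back the freedom for which that allowance was taken.

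**Working it through.** **Inputs from sections 11.3 and 11.6.** Performance goal 0.50; assumed ELS rate 0.68; two-sided alpha 0.05 (0.025 in the lower tail); power 80%; 58 evaluable; minimum pass 37/58; exact binomial test.

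**Input not in the documents.** m, the percentage points of all participants who are ELS failures, are cleared by another procedure before the endpoint imaging, and are scored as successes. I assume 0 to 15 points.

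**Step 1: reproduce the plan.** Normal approximation with null variance on the alpha term and alternative variance on the power term:

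n = [(1.960 × √0.25 + 0.842 × √(0.68 × 0.32)) / 0.18]² = 58.1, against 58 stated.

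Exact check with X ~ Binomial(58, p):

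- P(X ≥ 37 | p = 0.50) = 0.024
- P(X ≥ 37 | p = 0.68) = 0.798
- The exact lower 95% limit is 0.501 for 37/58 (the plan prints 0.502, with no effect on the rule) and 0.484 for 36/58. So 37 is the minimum pass.

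**Step 2: effect at the null.** With a true ELS-only rate of 0.50, the apparent rate is 0.50 + m, and the chance of passing is P(X ≥ 37 | 58, 0.50 + m). Half of the participants are ELS failures, so m points of all participants is 2m per cent of the failures.

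| m (points of all participants, assumed) | Share of ELS failures | Apparent rate | Chance of passing |
|---|---|---|---|
| 0 | 0% | 50% | 2.4% |
| 1 | 2% | 51% | 3.4% |
| 2 | 4% | 52% | 4.7% |
| 5 | 10% | 55% | 11.2% |
| 10 | 20% | 60% | 32.7% |
| 15 | 30% | 65% | 63.4% |

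**Step 3: effect in counts.** At the pass mark, one such participant decides the trial (37/58 passes, 36/58 fails). The expected count under the plan's assumption is 0.68 × 58 = 39.4. If 3 of 39 successes were rescued failures, the ELS-only result would be 39 − 3 = 36 of 58, a fail reported as a pass.

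**Step 4: after the fix.** Scoring rescue as failure leaves n and the pass mark unchanged, and the chance of passing at a true 50% is 2.4%. Power depends on what the 68% contains, which the documents do not say:

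- 68% is ELS-only: power 79.8%.
- 2 of the 68 points come from other procedures: P(X ≥ 37 | 0.66) = 69%.
- 5 of the 68 points do: P(X ≥ 37 | 0.63) = 51%.

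**The case against.** Nowhere does the plan say that a surgically cleared stone is an ELS success. The endpoint concerns participants successfully treated after up to two ELS treatments, and section 6.3.1 presents a second ELS treatment as the way to reach success. A fair reader could conclude that clearance by another procedure does not qualify, and the separate SAP may say so. This stands as far as wording goes: the defect is an omission, and it would be wrong to report that the plan has adopted such a rule. It does not close the gap, because the operational definition is imaging alone and the documents contain nothing to enforce the intent.

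The larger figures also need a lot of rescue. At the null, 15 points means that 30% of ELS failures are cleared elsewhere before the CT. Section 6.4 calls for one additional ELS treatment if needed, and a second treatment restarts the 30-day follow-up. That stands, and the low rows of the table deserve equal weight. The route is not closed, however, since section 6.3.1 allows for eligible participants who decline or are judged unsuitable.

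The per-protocol analysis, reported beside ITT, might seem a safeguard. It is a weak one: section 6.4 itself provides for other interventions, so a participant who has one may still count as treated according to the protocol.

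A reader might also infer an opposite error: that a participant with an admitted but untreated stone of 3 mm or more can never succeed, with a loss of power. The documents do not support that. The two-stone rule in 11.3 applies when ELS was performed on both stones and would be redundant if every stone counted. The synopsis bases retreatment on the treated stone or fragment. The natural reading is already limited to treated stones.

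**Conclusion.** The concern holds as a gap in the primary endpoint definition. Non-ELS intervention on the target stone is foreseen and recorded but not scored, and the literal definition would let it count as success. It should be closed before outcomes are examined, because in a single-arm study the choice would otherwise be made with the results in view, and one participant can decide the outcome.

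The size is conditional. At a true ELS-only rate of 50%, the chance of passing goes from 2.4% to between 3.4% and 63% for 1 to 15 points of rescue. These rates are assumptions. The results also assume 58 evaluable participants and that every rescued failure is scored as a success. They do not show that inflation of any given size will occur. Nor should the point be read as saying that the plan counts surgical clearance as ELS success by rule; it is silent. On untreated stones, only a clarification of wording is warranted.

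**What to change.** In the synopsis, 5.1 and 11.3, add that any non-ELS intervention to remove or fragment an ELS-treated stone or its fragments, between the first ELS treatment and the endpoint imaging, is scored as treatment failure whatever the imaging shows. Carry the same rule into the separate SAP. Report the number of such participants, with the imaging-only rate as a sensitivity analysis. This is a scoring rule only and changes no participant's care.

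As a clarification, state in the same places that success refers to the ELS-treated stone or stones and their fragments.

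The cost is a few sentences and no new data collection, since section 6.4 already puts these interventions on the eCRF. The observed success rate falls by exactly the rescued share, so if rescue is common the cost is not small. The sample size of 58 and the 37/58 rule stay. The sponsor should state whether the assumed 68% is an ELS-only rate: if so, power stays at 79.8%; if 2 or 5 points of it came from other procedures, power would be about 69% or 51%, and the sample size would need another look.

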6.5 Analysis of collected stone fragments

The collected stone fragments will be characterized by a qualified, central laboratory to determine stone chemical composition. The composition of the stone depends on the substances in the urine causing the stone. It may be made of just one chemical compound or have different chemicals in different layers. The analysis will be done in order to help identify the chemical composition of the stone, which in turn may guide better treatment options for participants with recurrent stone formation.

Table 2: Schedule of Events

Assessment	Screening	ELS Treatment	Days 1,2, and 3 after each ELS procedure	Day 7 (+/- 1) day after each ELS procedure	Day 14 (+/- 4) days after each ELS procedure	Day 30 (+/-4) days after last ELS procedure	Day 90 (+/-21) days after last ELS procedure
Site Visit	✓	✓	By telephone	By telephone	✓	✓	✓
Informed Consent	✓						
Inclusion / Exclusion criteria	✓						
Medical History	✓						
Pregnancy test	✓						
Physical Exam	✓				✓	✓	✓
Serum Creatinine	✓					✓	✓
Urinalysis and urine culture	✓				✓		
CT scan (non-contrast)	✓ (within 14 days of ELS)					✓	
X-ray (KUB)	✓ ¹				✓		
Ultrasound (renal bladder)					✓		✓
2 nd ELS Treatment Eligibility					✓ ²	✓ ²	
Participant urine straining, retaining stones for office visit		✓	✓	✓	✓	✓	
AE reporting		✓	✓	✓	✓	✓	✓
Complete Pain Questionnaire	✓ (within 1 day of ELS)		✓	✓	✓	✓	
Concomitant Meds (analgesics, alpha blockers, pain meds etc.)	✓	✓	✓	✓	✓	✓	✓
Complete Participant Satisfaction questionnaire						✓	
1: Recommended for participants suspected of having radiolucent stone(s) if CT scout film not available for use.							
2: ELS procedure repeated if CT scan shows stone/fragments of 3mm or more.							

Confidential

Page 20 of 1

Study of an Enhanced Lithotripsy System in the Treatment Of Urinary Stone Disease (STONES)

Version 2.0, July 10, 2019

7. RISKS AND BENEFITS

7.1 Potential Risks

The potential risks associated with the ELS procedure are expected to be similar or less than those of traditional SWL procedures used to treat urinary stones. Potential adverse events, which may be associated with the ELS and ELS Acoustic Enhancer material, and medications prescribed for use during these procedures include:

- Haematuria
- Pain or discomfort
- Skin redness where the treatment head is held against the body or from the belt that may be used to hold the treatment head in place
- Sensitivity/Tenderness over the treatment area
- Urinary blockage from stone fragmentation
- Bruising of tissue along the path of acoustic energy entering the body
- Urinary tract infection or inflammation
- Fever
- Mild cardiac arrhythmia could result from acoustic energy
- Bruising or damage to the kidneys, or tissue near the kidneys
- Allergic or anaphylactic reaction.
- Differential pressure risks include pressure from backflow of urine in the urinary tract system, and in rare cases rupture in the urinary tract

The procedure is also associated with potential anesthesia risks:

- Reaction to anesthesia
- Bleeding at anesthesia site
- As with any procedure performed with sedation or anaesthesia, there is risk associated that includes heart attack, stroke, and even death.

As with shock wave lithotripsy for urinary stones, the following adverse events may occur while being treated with ELS:

- Common (estimated as greater than 20% of patients)¹
 - There may be mild bleeding (including blood in the urine) or irritation from the ELS procedure. In rare cases, transfusion may be required to address bleeding.
 - There could be pain associated with the ELS sound wave energy effects and resulting stone fragments, with placement and movement of instruments in the urinary tract, or from other aspects of the procedure.
 - There could be skin redness around where the treatment head was held during the procedure, or irritation or bruising of the skin from the belt used to hold the treatment head in place during the procedure.

¹ Estimated occurrence rates are referenced from FDA, Center for Devices and Radiological Health: Guidance for the Content of Premarket Notifications (510(k)s) for Extracorporeal Shock Wave Lithotripters Indicated for the Fragmentation of Kidney and Ureteral Calculi (August 9, 2000)

- Occasional (estimated as 1-20% of patients)
 - As with any intervention to fragment kidney stones, urinary blockage with a need for alternative treatment may occur. Blockage could be due to stone fragments after the ELS procedure. Also, the stone may be incompletely fragmented, causing urinary tract blockage. – In the case of urinary blockage, an ureteral stent or a tube in the kidney (i.e. nephrostomy tube) may be needed in order to properly relieve the obstruction.
 - There may be bruising of tissue along the path of acoustic energy entering the body through the skin of the lower back.
 - The urinary tract could become infected, or existing urinary tract infection could become worse.
 - There is a possibility of fever.
 - There may be nausea or vomiting associated with administration of anesthesia or other aspects of the ELS procedure.
- Rare (estimated as less than 1% of patients).
 - In rare instances, there could be bruising or damage to the kidneys or tissue near the kidneys, resulting in pain and requiring further treatment. In very rare instances, this could require kidney removal.
 - In rare instances, the acoustic energy could result in mild cardiac arrhythmia (irregular heartbeats).

As with other treatments for urinary stones, sloughed tissue found in or on urinary stones may be released as a result of ELS treatment. In addition, malfunction of the equipment is a possibility and the procedure may need to be rescheduled.

Possible adverse events associated with the placement of the ELS Acoustic Enhancer material in the urinary tract during treatment with the ELS:

The major risk associated with ELS Acoustic Enhancer material is an allergic (less than 1 in a 10,000 patients) or anaphylactic reaction (less than 1 in 20,000 patients). The doctor will be there to address these complications in the unlikely chance that they occur.

The placement of the ELS Acoustic Enhancer follows a standard procedure used in a common diagnostic procedure (retrograde pyelogram). As such, there is a very low risk of adverse events associated with the differential pressures in the urinary tract arising during ELS Acoustic Enhancer placement. Differential pressure risks include pressure from backflow of urine in the urinary tract system, and in rare cases rupture in the urinary tract.

As with any procedures in which cystoscopes and other instruments are inserted into the urinary tract and materials placed using a cystoscope (small tube) into the urinary tract, in very rare cases, portions of the urinary tract could become inflamed or infected. There is also the risk of inadvertently pushing a urinary stone from the urinary tract into the kidney and of ureteral perforation from passage of the ureteral catheter.

Significant new findings that may affect the participant's safety or willingness to continue in the study will be communicated to the study doctors and study participants. An updated informed consent may be administered if appropriate.

7.2 Potential Benefits

ELS achieves cavitation and fragmentation of stones using extracorporeal acoustic energy at significantly lower intensities than that used by SWL systems. This results in the following expected benefits compared to SWL and other existing urinary stone interventions:

- Negligible renal parenchymal damage.
- Minimal or negligible damage to the urothelium.
- Treatment under light or moderate sedation, or light general anaesthesia (at investigator's discretion), rather than heavy sedation or general anaesthesia.
- Respiration and other small movements by the study participant during the ELS procedure should not negatively impact safety or efficacy.

7.3 Mitigation of Risks

Risk to study participants are mitigated in this study by the following:

- All investigations are conducted by investigators who are qualified by training and experience in the treatment of participants with urinary stones and specifically trained in the use of ELS.
- All assessments are procedures performed in the controlled context of a clinical trial.
- Monitoring of the clinical trial to ensure compliance and with a focus on potential safety issues.

8. ADVERSE EVENT REPORTING

8.1 Definitions

8.1.1 Adverse Events (AE)

Any untoward medical occurrence, unintended disease or injury, or untoward clinical signs (including abnormal laboratory findings) in study participants, users or other persons, whether or not related to the investigational medical device.

Any condition that was recorded as pre-existing is not an AE unless there is a change in the nature, severity or degree of the condition with respect to baseline.

